### 6.2. Efficacy evaluable set

The efficacy evaluable analysis set comprises all subjects who were randomised into the study, who received at least one dose of Chronocort® or standard therapy, and who have an evaluable week 24 17-OHP 24-hour hormone profile, and who have no major protocol violations.

It is difficult to conduct trials in this indication. This is the first comparative trial of a re-formulation of a standard therapy for CAH. The efficacy evaluable analysis set is therefore the primary analysis set for the evaluation of efficacy. The robustness of the conclusions will be assessed by repeating key efficacy analyses using the full analysis set.

The final determination of the membership of analysis sets will be made at a Data Review Meeting convened by the sponsor before database lock.

Subjects in the efficacy evaluable set will be analysed according to the actual treatment received.

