## **13.2 Analysis Sets**

The safety analysis set comprises all subjects who were randomised into the study and who subsequently received at least one dose of Chronocort® or standard therapy.

The full analysis set comprises all subjects who were randomised into the study, who received at least one dose of Chronocort® or standard therapy, and who have at least one post-randomisation 17-OHP 24-hour hormone profile.

The efficacy evaluable analysis set comprises all subjects who were randomised into the study, who received at least one dose of Chronocort® or standard therapy, and who have a week 24 17-OHP 24-hour hormone profile, and who have no major protocol violations.

The efficacy evaluable analysis set is the primary analysis set for the evaluation of efficacy. The final determination of the membership of analysis sets will be made at a data review meeting convened by the sponsor before database lock.

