### 13.6 Efficacy Analyses

#### 13.6.1 Primary Efficacy Analysis

The primary efficacy analysis is the comparison of the mean change from baseline to 24 weeks in the primary efficacy variable (natural logarithm of the mean over the 24-hour SDS profile for the natural logarithm of 17-OHP) between the Chronocort® treatment group and the standard therapy treatment group within the efficacy evaluable analysis set.

This is the primary efficacy analysis for this study. All other analyses of this outcome variable and all analyses of other efficacy variables are secondary or exploratory analyses.

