## 2. Study objectives and endpoints

### 2.1. Study objectives

#### 2.1.1. Primary objective

To demonstrate the superior efficacy of Chronocort® compared with standard glucocorticoid replacement therapy in the treatment of CAH based on 17-OHP.

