### 2.3.3. Multiple testing strategy

There will be no adjustment for multiple testing as the primary analysis will be considered the main analysis with the secondary and exploratory endpoints intended as support for the primary analysis.

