### **10.2. Protocol deviations**

Any deviations from the protocol will be reviewed at the Data Review Meeting following trial completion but prior to database lock. Each protocol deviation will be classified as either 'minor' (unlikely to affect trial outcomes) or 'major' (likely to affect outcomes). Any subject considered to have a major protocol deviation will be excluded from the Efficacy Analysis set (See 6.223). In addition, protocol deviations will be grouped into the following high-level categories:

- Inclusion criteria – subject failed to meet all inclusion criteria,
- Exclusion criteria – subject met at least one exclusion criteria,

---

 This differs from the +/- 10 minute window specified for investigators in the protocol so that results within a wider window can be considered acceptable for analysis.

- Study procedure – site or subject did not follow procedures specified in protocol,
- Titration – site or subject deviated from the titration process,
- Treatment – IMP not taken as per protocol,
- Local sampling – site performed endocrine sampling locally.

Protocol deviations will be listed and summarised by randomised treatment group, classification (major or minor) and protocol deviation category.

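### The primary superiority test uses the efficacy evaluable set, so it is not fully protected by randomisation; the full analysis set by randomised arm should be primary

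*SAP*

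**What the plan says.** The primary objective (SAP 2.1.1) is a superiority claim: "To demonstrate the superior efficacy of Chronocort® compared with standard glucocorticoid replacement therapy in the treatment of CAH based on 17-OHP". The design is open-label (protocol 8).

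Both documents place the primary 17-OHP ANCOVA in the efficacy evaluable set (protocol 13.2 and 13.6.1; SAP 6.2 and 10.5). Protocol 13.2 limits that set to treated, randomised subjects "who have a week 24 17-OHP 24-hour hormone profile, and who have no major protocol violations". SAP 6.2 adds that the profile must be evaluable, and opens its reasons with "It is difficult to conduct trials in this indication", followed by the remark that this is the first comparative trial of a re-formulation. It concludes: "The efficacy evaluable analysis set is therefore the primary analysis set for the evaluation of efficacy".

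SAP 10.2 defines a major deviation as one likely to affect outcomes and states: "Any subject considered to have a major protocol deviation will be excluded from the Efficacy Analysis set". Its categories cover eligibility failures and local sampling, but also titration, where "site or subject deviated from the titration process", and study drug not taken as the protocol requires.

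The same analyses are repeated in the full analysis set, which needs only one dose and one evaluable post-randomisation profile (SAP 6.1, 10.5, 10.6.1; protocol 13.6.2). Its rank is explicit. Protocol 13.6.1 says of the primary analysis: "All other analyses of this outcome variable and all analyses of other efficacy variables are secondary or exploratory analyses". SAP 2.3.3 says "the primary analysis will be considered the main analysis with the secondary and exploratory endpoints intended as support for the primary analysis". SAP 6.1 and 6.2 group both efficacy sets by treatment actually received; protocol 13.2 is silent on grouping.

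**The concern.** Randomisation makes the arms comparable as allocated. Removing subjects afterwards keeps that comparability only if removal is unrelated to outcome, or acts alike in both arms. Here removal is linked to outcome by the definition of a major deviation, and the arms differ in their opportunities to deviate. Chronocort has fixed clock times and food restrictions, while the comparator follows the site's usual practice (protocol 10.3). Midday titration advice has to be reallocated for every Chronocort subject, but on standard therapy only for those dosed twice daily (protocol 8, Dose Adjustment). The one drug-specific discontinuation event in protocol 11.5 is intolerance of Chronocort.

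Exclusions are not expected to be rare. The inevaluability allowance was raised from 7% to 15%, or 18 of 120 subjects, because of protocol deviations (protocol Appendix 10, Version 6.0). At stake is the trial's single confirmatory claim. The reasons in SAP 6.2 do not explain why a superiority test should leave out randomised subjects.

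**Working it through.** **Inputs from the plan** (protocol 13.8; SAP 5): falls of 0.78 and 0.20 on the log scale, so a difference of 0.58; SD 0.681; two-sided alpha 5%; 102 evaluable; 15% inevaluable; 120 randomised. No allocation ratio is given; 1:1 is assumed.

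**The plan's own figures.** 102/0.85 = 120, as stated. With 51 per arm, SE = 0.681 × √(2/51) = 0.1349 and the noncentrality is 0.58/0.1349 = 4.30. Noncentral t power is 98.9%, consistent with the stated figure of above 95%.

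**Bias from exclusions.** Suppose a fraction f of an arm is excluded and those subjects are k SDs worse than the retained ones. The retained mean is then better than the as-randomised mean by f × k × SD, so

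bias = (f_Chronocort × k_Chronocort − f_standard × k_standard) × 0.681.

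The splits and k are assumptions; the documents give neither. Under a true null, the chance of a two-sided p < 0.05 is the noncentral t tail with noncentrality bias/SE. The table uses the same k in both arms and 60 randomised per arm.

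| Excluded, Chronocort v standard | Retained | k | Bias | Noncentrality | Type I error |
|---|---|---|---|---|---|
| 15% v 15% | 51 v 51 | 0.5 or 1 | 0 | 0 | 5.0% |
| 17.5% v 12.5% | 50 v 52 | 0.5 | 0.05 × 0.5 × 0.681 = 0.017 | 0.126 | 5.2% |
| 17.5% v 12.5% | 50 v 52 | 1 | 0.034 | 0.252 | 5.7% |
| 20% v 10% | 48 v 54 | 0.5 | 0.10 × 0.5 × 0.681 = 0.034 | 0.252 | 5.7% |
| 20% v 10% | 48 v 54 | 1 | 0.068 | 0.504 | 7.9% |

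The non-zero biases are 3% to 12% of the planned 0.58 (0.017/0.58 and 0.068/0.58). Reversing the split gives the same size of bias against Chronocort.

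As a cross-check, a simulation (40,000 replicates) excluded subjects on a variable correlated with outcome. At 20% v 10% it gave 5.8% at correlation 0.3 and 7.4% at 0.5, in line with the table.

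**Power as randomised, 60 per arm.** Let 15% of Chronocort subjects have a mean fall m instead of 0.78. Then

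- difference = 0.85 × 0.78 + 0.15 × m − 0.20;
- Chronocort SD = √(0.681² + 0.15 × 0.85 × (0.78 − m)²); the standard arm keeps 0.681.

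With m = 0.20 (control fall only): difference 0.493, SD 0.712, SE 0.127, power 97.0%. With m = 0 (no fall): difference 0.463, SD 0.736, SE 0.129, power 94.4%. With no dilution, power is 99.6%.

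**The case against.** The best case for the plan is that the choice is open, agreed between protocol and SAP, and surrounded by safeguards. The SAP revision history lists no change to Section 6. The endpoint is a laboratory measure. Titration follows the same rules in both arms and is directed by a blinded physician (protocol 8). Deviations are classified and set membership is decided on data masked with dummy treatment labels (protocol 13.10; SAP 4.1). Exclusions are reported with reasons (SAP 6.3), deviations are summarised by randomised group (SAP 10.2), and Visit 4 assessments are sought from subjects who withdraw (protocol 11.4). The full analysis set repeat does not depend on the primary result, so a reader could see whether exclusions drive it.

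Most of this stands. It rules out two stronger readings. A reader might infer that the sponsor can pick subjects by arm; the masking provisions speak against that. A reader might also infer that the result will favour Chronocort. The documents give no arm-specific exclusion rate and no link between exclusion and outcome. Lopsided assumptions do yield large figures: 25% v 5% with correlation 0.5 simulates to 13.4%. Nothing in the plan points to such a split.

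What does not stand is the idea that masking settles the matter. It prevents knowing selection, but not deviations that themselves arise differently by arm. Nor can a secondary repeat carry the claim when the stated hierarchy rests it on the evaluable set.

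**Conclusion.** The concern holds as a point of structure. The only confirmatory comparison conditions on events after randomisation that may depend on the arm, while the analysis closer to the randomised comparison ranks below it. It does not follow that the primary comparison is biased: with equal, equally informative exclusions the calculated bias is zero, and otherwise it can run either way. Under the moderate imbalances assumed here, two-sided type I error is 5.2% to 7.9% instead of 5%.

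This should be fixed, since the remedy is cheap, but it is not a fatal defect. A reader might infer that the trial cannot support its claim as planned. The documents do not show that, because the size of the problem is unknown and the full set repeat would help to reveal it. Grouping by treatment received adds to the point only if a first dose differs from the allocation.

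The sample size does not require the restriction in the milder dilution case (97.0%). In the worse case (94.4%) power falls just short of the stated 95%.

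**What to change.** Before unblinding, amend protocol 13.2, 13.6.1 and 13.6.2 and SAP 6.1, 6.2, 10.5 and 10.6.1 so that:

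- the 17-OHP ANCOVA in the full analysis set, grouped by randomised arm, is primary;
- the efficacy evaluable set is supportive.

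For subjects without a week 24 profile, keep the latest-available-profile rule of SAP 9.1 and state that it is the primary rule. Its present wording covers withdrawn subjects, so extend it to anyone else in the full set whose week 24 profile is missing. Because the rule can pick up a week 4 profile, taken before any scheduled titration, add one named sensitivity analysis. Multiple imputation from baseline, stratum and the week 4 and 12 profiles is one example. Report by arm the randomised subjects with no post-randomisation profile, and include them in that analysis.

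**Cost.** This changes the primary analysis, so it is unlikely to pass as a minor change under protocol 13 and would need the approvals in protocol 14.11.2. It is late: SAP 9.3.3 (version 4.0) describes the Data Review Meeting as already held, before lock and unblinding. The amendment must therefore be documented as made blind. The full set hormone tables are already planned (SAP 14.1), so the programming is mainly a re-run by randomised arm plus the sensitivity analysis. The estimate may be diluted, and power above 95% is not assured.

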### 6.3. Safety analysis set

The safety analysis set comprises all subjects who were randomised into the study and who subsequently received at least one dose of Chronocort® or standard therapy.

Subjects in the safety analysis set will be analysed according to the actual treatment received.

A summary will be produced of the number of subjects in each analysis population, together with reasons for exclusion from each analysis set.

## 7. Treatment comparisons

### 7.1. General

The comparison in all analyses will be between the Chronocort® treatment group and standard glucocorticoid replacement therapy.

For the stratified secondary and exploratory analyses and the stratified analysis of the primary endpoint, comparisons will be presented for subgroups defined by the pre-baseline standard treatment.

### 7.2. Data display (treatments and other subgroups) descriptors

The treatment group descriptors to be used in outputs are listed in Table 1 below. The full data display descriptor is preferred, although the abbreviated option in the third column may be used if there is not enough space on the page.

In general, where subgroups are presented in a table as three separate columns (optionally together with a “Total” column), then these columns should preferably be displayed using the full treatment group descriptor spanning all three columns (four including a “Total” column) as a “super-header” and either the full or abbreviated stratification descriptor underneath.

*Table 1: Treatment group and stratification subgroup descriptors*

Treatment group/stratification factor	Full data display descriptor	Abbreviated data display descriptor
Treatment groups		
Chronocort® (Any pre-baseline standard therapy)	Chronocort	Cct
Standard glucocorticoid replacement therapy (All groups combined)	Standard GC therapy	SGC
Stratification factors (subgroups)		
Pre-baseline therapy of hydrocortisone only	Hydrocortisone only	Hydro
Pre-baseline therapy of prednisone or prednisolone (alone or in combination with hydrocortisone)	Prednisone or Prednisolone	Pred
Pre-baseline therapy of dexamethasone (alone or in combination with any other glucocorticoid)	Dexamethasone	Dex
Combined treatment group/subgroups		
Chronocort® with pre-baseline therapy of hydrocortisone only	Chronocort - Hydrocortisone only	Cct - Hydro

Chronocort® with pre-baseline therapy of prednisone or prednisolone (alone or in combination with hydrocortisone)	Chronocort – Prednisone or Prednisolone	Cct - Pred
Chronocort® with pre-baseline therapy of dexamethasone (alone or in combination with any other glucocorticoid)	Chronocort - Dexamethasone	Cct - Dex
Standard glucocorticoid replacement therapy, hydrocortisone only	Standard GC - Hydrocortisone only	SGC - Hydro
Standard glucocorticoid replacement therapy, prednisone or prednisolone (alone or in combination with hydrocortisone)	Standard GC – Prednisone or Prednisolone	SGC - Pred
Standard glucocorticoid replacement therapy, dexamethasone (alone or in combination with any other glucocorticoid)	Standard GC - Dexamethasone	SGC - Dex

## 8. General considerations for data analyses

All statistical analyses will be performed using the software package SAS® version 9.1 or higher.

### 8.1. Standard summary statistics

The standard summary statistics for continuous baseline and outcome variables are: N, mean, standard deviation (SD), median, quartiles, minimum and maximum. The standard summary statistics for categorical baseline and outcome variables are: count and proportion (expressed as percentage). Geometric mean and coefficient of variation will also be presented for variables which will subsequently be log-transformed during the analysis.

### 8.2. Standard comparison methods

In general, continuous variables will be compared across treatment groups using a Normal analysis of covariance (ANCOVA) linear model including pre-baseline standard therapy and, if appropriate, the baseline assessment of the variable as covariates in the model. In the case of change-from-baseline variables, baseline will always be included as a covariate.

Binary variables, such as response, will be compared using logistic regression with adjustment for covariates as in the continuous data case.

### 8.3. Statistical significance and multiple testing strategy

All significance probabilities will be reported as two tailed. Confidence intervals will be reported as 95% two-sided. There will be no adjustment for multiple testing.

### 8.4. Strata and covariates

Pre-baseline standard therapy refers to the standard glucocorticoid replacement therapy the subject was receiving for at least 6 months prior to joining the study, namely the strata used for randomisation:

- Hydrocortisone only
- Prednisone or prednisolone, alone or in combination with hydrocortisone
- Dexamethasone only or in combination with any other glucocorticoid

## 8.5. Examination of subgroups

Additional exploratory and sensitivity analyses of the assessment of the efficacy results in subgroups may be required if appropriate.

## 9. Data handling conventions

### 9.1. Premature withdrawal and missing data

Missing 17-OHP and A4 values (including those considered missing due to being taken outside the permitted time window) within the 24-hour hormone profile will be imputed by linear interpolation of the two closest non-missing measurements to the scheduled missing time point (including out-of-window measurements). Further details are given in Section 9.3.3. In the event that several values are missing from a single profile, a decision will be made about the validity of the whole profile at the Data Review Meeting on a case-by-case basis.

For efficacy analyses based on the Week 12 and Week 24 visits, subjects who have withdrawn from the study will be assessed on the basis of the latest available 24-hour profile. This is a conservative procedure as subjects enter the study already receiving a suitable dose of their standard therapy.

When calculations must be based upon incomplete dates the following process will be used. If year is missing do not impute. The value should be considered missing. If year is populated but both month and day are missing then the date defaults to 1st July. If day only is missing then the day defaults to the 15th of the month.

For adverse events and concomitant medications, if year is missing do not impute. If start year is populated but both month and day are missing, or if month is missing and day is present, then the date defaults to 1st January. If day only is missing then the day defaults to the 1st of the month. If end year is populated but both month and day are missing, or if month is missing and day is present, then the date defaults to 31st December. If day only is missing then the day defaults to last day of the month. For definition of treatment emergent and ongoing, if partial dates are only available for start and end, then we are conservative and assume treatment emergent/ongoing.

For those subjects with one middle dose then this is considered as “middle 1”, and middle2 is blank for all subjects except those with a second middle dose.

Exploratory and sensitivity analyses will be performed to assess the effect of any missing data on the efficacy conclusions. This will be discussed at the Data Review Meeting and a decision will be made on the appropriate analyses.

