#### **STATISTICAL METHODS:**

The Statistical Analysis Plan (SAP) must be finalised before any subject is randomised into the trial.

Efficacy: The primary efficacy endpoint is the change from baseline to 24 weeks in the primary efficacy variable (natural logarithm of the mean over the 24-hour SDS profile for 17-OHP). The primary efficacy endpoint will be compared between treatment groups within a Normal linear analysis of covariance (ANCOVA) model with baseline treatment category and baseline SDS as covariates. Exploratory analyses will investigate the sensitivity of the results to the transformation of the endpoint and to the form of the model. Secondary endpoints will also be analysed as a change from pre-randomisation baseline to end-of-study. To ensure that the treatment effect of Chronocort® is not all as a result of non-hydrocortisone based regimes being different in achieving control, the effect of Chronocort® within baseline treatment subgroups will be presented.

Safety: Summary vital signs change from baseline data will be presented in tabular form, by dose level across time, with N, mean, standard deviation (SD), median, quartiles, minimum and maximum as appropriate.

Summary ECG (heart rate, PR interval, QRS width, QT interval and QTC interval) change from baseline data will be presented in tabular form, by dose level across time, with N, n, mean, SD, median, minimum and maximum as appropriate.

AEs will be coded using the latest version of the MedDRA drug dictionary. Data will be summarised using preferred term and primary system organ class. Only treatment-emergent AEs, being events with an onset at or after the first administration of study drug, will be presented in summary tables. Where changes in severity are recorded in the eCRF, the most severe incidence of the AE will be reported in the tables. Rates will be calculated as the proportion of subjects with at least one AE related to the number of subjects treated in each treatment group. Frequency tables will be provided concerning severity and drug relationship.

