### ***12.2 Adverse Event Collection***

AEs will be collected for all subjects from the time of consent up to phone call T4 (30 days ± 3 days) following the last visit or, if applicable, the Early Withdrawal visit. Any ongoing AEs post study will be followed to resolution or stabilisation if resolution is not expected. Only treatment emergent AEs will be included in the main safety analysis: other AEs will be listed.

Details of any AEs, signs, and symptoms will be collected, including details of onset, resolution, frequency, severity, seriousness, relationship to the drug, effect on the study drug, treatments administered, and outcome. All AEs will be followed, whenever possible, until it returns to the baseline condition or becomes stable with no further change expected. In the event of any abnormalities considered to be clinically significant by the investigating physician, subjects will be followed up with appropriate medical management until values are considered to be clinically acceptable. Referral or collaborative care will be organised if required.

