### 11.2. Adverse events

All AEs, in terms of MedDRA system organ class (SOC) and preferred term (PT), will be listed and summarised descriptively by count (n) and percentage (%) for each treatment group. For the purpose of the CSR, only AEs up to the follow up-telephone call after the week 24 visit will be included in summaries. Any AE occurring before randomised Chronocort®/ standard glucocorticoid replacement therapy treatment (i.e. before the first dose of randomised treatment on Day 2 of visit 1) will be included in listings but not summaries, unless there is an increase in severity occurring after the start of treatment. Similarly, any AE occurring after the last day of study treatment for subjects who enter the extension study or the last day of study treatment plus 30 days for subjects who do not enter the extension study will be listed but not summarised.

All reported AEs will be listed along with the study day of onset, resolution, duration, seriousness, severity, action taken with study drug, relationship to study drug, treatments administered and outcome. Frequencies and percentages of subjects reporting each PT will be presented (i.e. multiple events per subject will not be accounted for, apart from on the episode level summaries). Where severity is displayed, if a subject has more than one AE of the same term, the maximum severity will be used.

An overview table of AEs displaying the number of AEs by treatment group as well as the number and percent of subjects with the following categories will be produced:

- Any AE
- Any AE causally related to IMP

- Any AE leading to sick day rules
- Any AE leading to sick day rules causally related to IMP
- Any AE leading to Addisonian crisis
- Any AE leading to Addisonian crisis causally related to IMP
- Any AE leading to unexpected therapeutic benefit
- Any AE leading to unexpected therapeutic benefit causally related to IMP
- Any AE leading to death
- Any AE leading to death causally related to IMP
- Any AE leading to discontinuation
- Any AE leading to discontinuation causally related to IMP
- Any SAE
- Any SAE causally related to IMP
- Any SAE leading to discontinuation
- Any SAE leading to discontinuation causally related to IMP.

The number and percent of subjects experiencing each AE will be summarised by treatment, SOC and PT for the following:

- All AEs
- All serious adverse events (SAEs)
- SAEs with outcome of death
- AEs leading to discontinuation of study treatment

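### SAP 9.1 does not say clearly whether an adverse event with a partial start date but a complete or absent end date is treatment emergent; read literally, some on-treatment events are backdated to before the first dose

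*SAP*

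**What the plan says.** SAP 9.1 has one paragraph on incomplete dates for AEs and concomitant medications.

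- Year missing: "For adverse events and concomitant medications, if year is missing do not impute".
- Month missing: the condition is "If start year is populated but both month and day are missing, or if month is missing and day is present", and the start becomes 1 January of the recorded year.
- Day missing: "If day only is missing then the day defaults to the 1 st of the month".
- Classification: for treatment-emergent and ongoing status, "if partial dates are only available for start and end, then we are conservative and assume treatment emergent/ongoing".

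No sentence deals separately with a partial start and a complete end date, or with a partial start and no end date because the event continues.

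The classification decides what is tabulated. The protocol synopsis (Statistical Methods, Safety) says: "Only treatment-emergent AEs, being events with an onset at or after the first administration of study drug, will be presented in summary tables". SAP 11.2 says that an AE occurring before randomised treatment "will be included in listings but not summaries, unless there is an increase in severity occurring after the start of treatment". Protocol 12.2 states that "AEs will be collected for all subjects from the time of consent up to phone call T4", so the database will also hold genuine pre-dose events and the two kinds must be separated.

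**The concern.** The start-date defaults always choose the earliest possible date. For treatment-emergent status that is the unfavourable direction, because it can move an onset from after the first dose to before it. The classification sentence is evidently meant to prevent this, but as worded it depends on the end date being partial too. Better information then gives the less cautious answer: an AE that started in May and ended in June (day unknown) is protected, while the same AE with a recorded end of 30 June is not.

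At stake is the content of the AE summary tables. With the day missing, the exposed period is the rest of the calendar month of the first dose. After randomisation the next scheduled AE enquiry is Visit 2 at week 4 (Protocol Table 1), so an early event may be dated from memory and a missing day is plausible. Two programmers could also produce different tables from the same sentence.

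**Working it through.** The plan states no figure for this rule, so there is none to reproduce. The check has two parts.

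**1. Cases side by side.** First dose on 15 May. The literal reading applies the protection only when start and end are both partial. The respective reading takes a partial start to mean treatment emergent (TE) and a partial end to mean ongoing.

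| Recorded start | Recorded end | Imputed start | Literal | Respective | What the known parts show |
|---|---|---|---|---|---|
| May | 30 June | 1 May | pre-treatment | TE | may have begun on treatment |
| May | none, ongoing | 1 May | pre-treatment | TE | may have begun on treatment |
| May | June | 1 May | TE | TE | may have begun on treatment |
| June | 30 June | 1 June | TE | TE | began on treatment |
| March | April | 1 March | TE | TE | over before first dose |
| March | 10 April | 1 March | pre-treatment | TE | over before first dose |

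Rows 1 and 2 are the loss on the literal reading. Row 4 shows its limit: an onset in a later month is unaffected. Row 5 is an error in the other direction on both readings, and row 6 is that error on the respective reading only.

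**2. Share misclassified on the literal reading, among on-treatment onsets to which the protection does not apply.** Assumptions: first-dose date uniform over a 365-day year; true onset uniform over study days 2 to 170 (169 days; the week 24 visit is at target days 169 and 170, SAP 9.3.1).

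*Day missing.* The imputed start precedes the first dose when onset is in the first-dose month and the first dose was not on the 1st. In a month of d days, a first dose on day j (j = 2 to d) exposes d − j onset days, which sum to (d − 1)(d − 2)/2.

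- 31 days: 30 × 29/2 = 435, times 7 months = 3,045
- 30 days: 29 × 28/2 = 406, times 4 months = 1,624
- 28 days: 27 × 26/2 = 351, times 1 month = 351
- Share = 5,020 / (365 × 169) = 5,020 / 61,685 = **8.1%**

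By first-dose date it runs from 0% (first dose on the 1st or the last day of a month) to 29/169 = 17.2% (first dose on the 2nd of a 31-day month).

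*Month missing.* The imputed start precedes the first dose when onset is in the first-dose year and the first dose was not on 1 January. First doses on days 2 to 196 of the year (195 dates) have all 169 onset days in that year, so the share is 1. For the remaining 169 dates the share falls from 168/169 to 0, summing to (168 × 169/2)/169 = 84. Share = (195 + 84)/365 = **76.4%**, ranging from 0% to 100% by first-dose date.

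*Sensitivity.* Extending onsets to day 200, to cover the 30-day follow-up, gives 5,020/(365 × 199) = 6.9% and (165 + 99)/365 = 72.3%. If onsets cluster early (assumed exponential, mean 42 days), the shares are about 28% and 89%.

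*Overall effect.* This needs the fraction of AEs with a missing day and no protection, which the documents do not give. If it were 2% to 10% (assumed), the loss would be 0.02 × 8.1% = 0.16% to 0.10 × 8.1% = 0.81% of on-treatment AEs. Using 28% as well, the upper end is 0.10 × 28% = 2.8%, which multiplies two unfavourable assumptions.

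**The case against.** The strongest reply is that the sentence is meant respectively: it is introduced for the definition of treatment emergent and ongoing, pairs start and end with those two terms, and calls itself conservative. The date defaults would then serve only the listings, which need an onset day and a duration. This is a fair reading and no event is lost under it. It stands as a possibility, but nothing in the SAP selects it, and it leaves rows 5 and 6 of the table wrong.

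A reader might infer that all such AEs vanish from every summary. They do not. Onsets after the first-dose month (day missing) or year (month missing) stay treatment emergent, an event that worsens after treatment starts is still summarised, and every event is listed.

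A reader might also infer that the tables of serious AEs and sick-day events are the most exposed. Protocol 12.9 points the other way: serious AEs are reported within 24 hours on a form that asks for date and time of occurrence, and adrenal crises and events triggering sick day rules are reported in the same manner. Partial starts should be least common there.

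Finally, a reader might infer a bias between the arms, since Chronocort subjects change formulation in the first weeks and controls do not. The rule is the same in both arms, Protocol 12.3 requires equal reporting, and the documents show no difference in early event rates or date completeness. The arm effect is conjecture.

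Unknown months should also be rare, because AEs are asked about at every visit and at the dose-adjustment calls. The 76% figure therefore applies to what is likely a very small group.

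**Conclusion.** The point holds as a gap in the rule. On the literal reading, an AE with a partial start and a complete or absent end date is called pre-treatment when it began after the first dose in the same calendar month (day missing) or year (month missing). On either reading, an AE with partial dates that clearly ended before the first dose is called treatment emergent.

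The shares of about 8% and 76% rest on uniform first-dose and onset dates, and apply only to AEs that the protection does not cover. The number of AEs affected cannot be derived; the effect on the safety tables is probably small, and the primary efficacy analysis is untouched. It is still worth settling, because a rule that decides which AEs are tabulated should have one meaning before the tables are run.

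**What to change.** Replace the last sentence of that paragraph in SAP 9.1 with:

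> An AE with an incomplete start date is treatment emergent unless the known parts of its start date, or its end date, show that it began or ended before the first dose, whatever the status of the end date. The 1st-of-month and 1-January defaults are not used for this classification. Where the AE is treatment emergent under this rule and the partial start is consistent with the month (or year) of first dose, the start is imputed as the date of first dose.

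The condition in the last sentence matters. With first dose on 15 May, an AE with start May and end 5 May is pre-treatment and must not be given a start of 15 May, after its own end. The sentence being replaced also settles ongoing status when the end date is partial, so that part should be kept as a sentence of its own.

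The cost is a short change to the SAP and to the date-imputation program. The downside is that a few events that began between consent and first dose may be counted as treatment emergent, which is the conservative direction the SAP says it wants.
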